13.5.2 Interim Analysis of Safety Data

Not applicable.

13.5.3 Futility Analysis

Not applicable.

13.6 Statistical Hypotheses

Our hypothesis is that CD28 expression in the allergen specific (CD154+ or tetramer+) T-cell activation towards a Th1/ anergic state at week 52 DBPCFC relative to baseline will be significantly decreased among those who achieve desensitization versus those who do not.

13.7 Sample Size Considerations

We have excellent power to address our primary objective using the ANCOVA methods. For example, assuming that 81% of subjects achieve desensitization at week 52, we will have approximately 58 responders and 14 non-responders. Given this sample size and group distribution, assuming 2 repeated measurements having a compound symmetry covariance structure, that the correlation between observations on the same subject is 0.5, and assuming a standard deviation for change in CD28 expression on the arc-sin scale at week 52 of 0.90, we have 87% power to detect a difference in change in CD28 expression between responders versus non-

responders of 0.75 on the arcsin scale. If we assume 85% are desensitized, corresponding to 61 responders with assumptions similar to those made above, we have 82% power to detect the same difference. If we consider a 15% missing data on CD28 expression on week 52, we would have 80% power to detect the same change in CD28 expression, assuming 81% are desensitized. If the standard deviation is assumed to be higher – for example due to missing data -- and is as high as 1.1 on the arcsin scale for example, we have 77% power to detect a difference in change between responders and non-responders of 0.85 on the arcsin scale, assuming 81% are desensitized. If we consider a 20% missing data, we would have 78% power to detect the change of 0.85 on the arcsin scale. The treatment effect is assumed to be the same between two foods, however, to ensure that we have enough shrimp allergic participants to detect the SU, we will try to enroll at least 14 participants with shrimp allergies.

Our phase 2 clinical study is designed to provide preliminary data on the feasibility of correlating mechanistic features with a number of clinical phenotypes of interest. We propose consistent, rigorous entry criteria as well as standardized, reproducible methods for OIT. This level of participant characterization should enhance the ability to determine the important epitopes and interpret any change in responses following OIT. For comparison, we will include naturally tolerant individuals and allergic individuals who are not treated. Naturally tolerant individuals are defined as individuals who had clinically diagnosed food allergies (by OFC) who then lost those food allergies over time and have a verified negative OFC upon repeat OFC for that food allergen. The sample size calculations are based on our prior work and successful outcomes of clinical trials. The sample size has been selected in consideration of the needs to acquire a sufficiently large set of immunophenotypes via targeted RNA-Seq, CyTOF, and TCR sequencing measurements to significantly differentiate desensitization vs SU vs clinical failure.

Our sample size provides adequate information to explore whether mechanistic features or changes in mechanistic features can discriminate participants into clusters of clinical interest including response to OIT (desensitization vs SU), type of allergy (cashew or shrimp), severity of allergic reaction at baseline, and natural tolerance vs persistence of FA. For example, in a prior study of $n=5$, in which we tested CD154+ T cells and tetramer + T cells over time during peanut immunotherapy, we found that there was a change of a 30% increase in Th1/anergy and Treg parameters (Ryan, et. al. PNAS 2016; Syed, et al. 2014) so this provides rationalization for choosing at least a 20% change compared to baseline in our primary endpoint.

All participants will be HLA-typed. Given the HLA types that we have sequenced and found in our patient populations, we expect that we will be able to perform tetramer sorting of single cells in at least 60% of the participants. We plan to perform bulk sorting on activation-positive T cells (after epitope stimulation) for all participants.

Finally, we believe it is important to test similarities and differences in T cell responses among food allergens, particularly those in common foods associated with near-fatal anaphylaxis, such as cashew and shrimp. We believe it will not be difficult to recruit patients or obtain data on these distinct allergens, since the tools are developed for epitope-specific use based on distinct peptides derived from the different food allergens. However, we will approach these studies in a stepwise manner, starting with one food. If either the recruitment of suitable participants or laboratory analysis are more arduous than anticipated, we will have complete data on at least one or two of the three foods.

14. Identification and Access to Source Data

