Any participant that terminates early or who reaches week 58 or the optional Week 64 , will be referred to an allergy practitioner for further follow up and clinical care.

Mechanistic controls:

We will compare our results against non treated mechanistic controls with similar clinical characteristics. These mechanistic controls are historical controls that are allergen-matched and clinically matched as best as possible. These participants consent for blood sampling under a separate IRB-approved consent.

Figure 2. Study Flow Chart

Timepoint/Visit	Screen	Week 0 / Day 1	Every 2 wks (Weeks 0-28 or until maintenance reached)	Week 52	Week 58 /End of Study	Week 64 (Optional)	
Informed Consent		x					
Medical History	X						
Physical Assessment	X	X	X	X	X	X	
Con Meds	X	X	X	X	X	X	
Adverse Events	X	X	X	X	X	X	
Specific IgE/IgG4*	X			X	X	X	
Skin testing	X			X	X	X	
Blood for T cell studies*	X	X		X	X	X	
Urine pregnancy test	X						
Lung Function	X	X	X	X	X	X	
Diaries		X	X	X	X	X	
Inject Epi training	X			X	X		
Fecal samples	X			X	X		
DBPCFC	X			X TEST DESENSITIZATION	X TEST SU	X TEST SU	
OIT (cashew or shrimp)		X	X				
QOL questionnaires*	X	X		X	X		

*If unable to perform at both screening and Week 0, sample from either visit will suffice.

In case of unforeseen circumstances that make an in-person visit in clinic difficult, doses may need to be sent to the participant's home.

We plan to identify the basic immune mechanisms monitored by epitope-specific T cell methods which could potentially explain the differences in the effects of OIT in individuals who do or do not become clinically tolerant and to determine whether immune monitoring can predict the safety and efficacy outcomes in OIT protocols, and predictors of re-emergent allergic reactivity. After initial screening and enrollment, there are three phases of the study (Figure 1):

- Dose escalation and Build up Phase
- Maintenance phase
- Withdrawal phase

Treatment Failures:

- Treatment failures will be defined as those participants who withdraw or who are withdrawn due to unacceptable side effects of OIT by week 52
- If participants demonstrate moderate or severe clinical reactivity (Appendix 3) in DBPCFC at week 58, they will be considered desensitized but SU failures.

All participants who start home dosing of OIT will be considered in statistical analyses of the intent-to-treat population.

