3.4. Exploratory Clinical Objectives

- Comparing the proportion of participants who become desensitized vs all others (i.e. treatment failures) at week 52 DBPCFC.
- Comparing the proportion of participants who reach SU vs desensitized but SU failures at week 58 DBPCFC.
- Comparing changes in the transcriptomes and phenotypes of tetramer+ T cells from baseline to 52 weeks, 58 weeks, and to 64 weeks.

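### The 80% power with 15% missing CD28 in 13.7 assumes losses roughly proportional to the 81/19 split, although they may concentrate in the 14 or so non-passers; the 77% and 78% figures cannot both hold at one SD

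*Combined protocol and SAP*

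**What the plan says.** Section 13.7 opens with "We have excellent power to address our primary objective using the ANCOVA methods". It continues: "assuming that 81% of subjects achieve desensitization at week 52, we will have approximately 58 responders and 14 non-responders". With an SD of change of 0.90 on the arcsin scale and a within-subject correlation of 0.5, it gives 87% power for a difference of 0.75, or 82% with 61 responders. On missing data it says: "If we consider a 15% missing data on CD28 expression on week 52, we would have 80% power to detect the same change", still with 81% desensitized. For an SD as high as 1.1 it says "we have 77% power to detect a difference in change between responders and non-responders of 0.85 on the arcsin scale". The next sentence reads: "If we consider a 20% missing data, we would have 78% power to detect the change of 0.85 on the arcsin scale". That sentence does not restate the SD.

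The primary comparison is between those who pass the week-52 challenge and all others (13.2.1). Section 3.1 says: "Treatment failures will be defined as those participants who withdraw or who are withdrawn due to unacceptable side effects of OIT by week 52". It also says: "All participants who start home dosing of OIT will be considered in statistical analyses of the intent-to-treat population". Section 3.4 treats all others and treatment failures as the same group: "Comparing the proportion of participants who become desensitized vs all others (i.e. treatment failures) at week 52 DBPCFC".

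Under 6.5 and 11.4, staying in the study to week 58 after stopping OIT is permitted, not expected, and 11.4 lets the follow-up visits consist of a skin test, a blood draw or both. Section 11.3 rules out replacement once home dosing has begun.

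**The concern.** The primary contrast rests on about 14 people. A week-52 CD28 value lost from that group costs far more power than one lost from the 58. A passer has attended the week-52 visit, where the mechanistic blood is drawn (8.3). Someone who withdrew earlier for side effects is a non-passer and may have no week-52 sample. One mechanism therefore both puts a participant in the small group and makes the outcome likelier to be missing. Section 13.7 gives one power figure for 15% missing and does not say how the losses divide.

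The second problem is internal to 13.7: for the same difference, stated power goes up by a point in the sentence that introduces a 20% loss.

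A null primary result would be read against a claim of excellent power and a stated 80%, when the analysis might have had clearly less.

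**Working it through.** **Inputs.** All are from 13.7 and 13.4.2: ANCOVA of change on baseline CD28 and a pass indicator, two-sided 0.05; difference 0.75 with SD of change 0.90, or 0.85 with SD 1.1; correlation r = 0.5; 72 participants, 81% passing.

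**Method.** Under compound symmetry with r = 0.5, the variance of change is 2σ²(1 − 0.5) = σ². Adjusting for baseline leaves a residual SD of SD × √(1 − 0.5²): 0.90 × 0.866 = 0.779, or 1.1 × 0.866 = 0.953. The standard error is residual SD × √(1/n₁ + 1/n₀). Power comes from the noncentral t with n − 3 degrees of freedom.

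**Reproducing the plan.**
- 58/14: SE = 0.779 × 0.298 = 0.232; noncentrality 0.75/0.232 = 3.23; power 89.0% (stated 87%).
- 61/11: 82.5% (stated 82%).
- 15% missing: 0.15 × 72 = 10.8, taken as 11, leaving 61. At 81%, 61 splits as 49.4/11.6: 50/11 gives 81.1% and 49/12 gives 83.6% (stated 80%).

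The stated 80% is therefore a near-proportional-loss figure.

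**Same 11 losses, divided differently** (difference 0.75, SD 0.90):

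| Non-passers among the 11 lost | Passers/non-passers left | Power |
|---|---|---|
| 0 | 47/14 | 87.4% |
| 1 | 48/13 | 85.7% |
| 2 | 49/12 | 83.6% |
| 3 | 50/11 | 81.1% |
| 4 | 51/10 | 78.1% |
| 6 | 53/8 | 70.4% |
| 8 | 55/6 | 59.5% |
| 11 | 58/3 | 35.9% |

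Section 13.7 also leaves open what the 81% refers to. If it applies to all 72, anyone who leaves before week 52 comes out of the other 14. If it applies only to those with data, about 49 of 72 (68%) are passers with data, and the withdrawn drop out of the comparison with all others.

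**The 77% and 78% pair** (difference 0.85). For 20% missing, 0.20 × 72 = 14.4, taken as 14, leaving 58; 81% of 58 gives 47/11.

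| Case | Split | ANCOVA power |
|---|---|---|
| SD 1.1, complete data | 58/14 | 84.0% |
| SD 1.1, 15% missing | 49/12 or 50/11 | 77.8% or 75.0% |
| SD 1.1, 20% missing | 47/11 (46/12 with favourable rounding) | 74.4% (77.2%) |
| SD 0.90, 20% missing | 47/11 | 89.2% |

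At a fixed SD and a fixed 81% split, power must fall as data are lost: from 84.0% to 74.4% with complete data as the start, or from 77.8% to 74.4% if the 15% loss is the start. Reverting to SD 0.90 removes the contradiction in direction, but the planned analysis then gives about 89%, not 78%.

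**The case against.** The case against has real force in four places.

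*Being a non-passer is not the same as having no sample.* Section 8.3 schedules a challenge and mechanistic blood for all at week 52, and Appendix 1 lists T-cell blood there. Section 3.1 asks those tolerating at least 300 mg to return at week 52 for blood and/or skin tests. Under 6.4.2, those who fail escalation stay in the study as maintenance failures. Ordinary challenge failures are thus sampled on schedule. A reader might infer that side-effect withdrawals lack week-52 CD28 by definition; the documents do not support that. What stands is that for those who stop OIT the sample is optional, and that the sample in 6.4.2, about one week after stopping build-up for repeated reactions, is not a week-52 value.

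*The 15% need not be side-effect withdrawals.* It can include missed draws or failed assays in passers. In the earlier study described in 1.4, 12 of 50 withdrew and none of the listed reasons is a side effect. This supports treating concentration as a risk, not a forecast.

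*The 80% tolerates some imbalance.* It would be too strict to say that it holds only if losses fall evenly: three non-passers among the 11 losses still gives 81%.

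*The 77% may not assume complete data.* Section 13.7 introduces SD 1.1 as possibly reflecting missing data. Carrying the 15% loss forward gives 77.8%, so a reader who infers that 77% should be 84% goes further than the text allows. A two-sided t-test on the change score at SD 0.90 and 47/11 gives 79.1%, near the stated 78%, but it gives 78.8% where the plan states 87%, so it cannot be the common method. None of this lets 77% and 78% stand together at one SD.

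**Conclusion.** The concern holds in limited form. The 80% in 13.7 depends on an unstated assumption that losses are roughly proportional. Power falls below 80% once four of the 11 missing values belong to non-passers, and is about 60% to 78% when four to eight do. A reader might take 36% as the power to expect; it is the worst case, needing 11 of 14 non-passers lost and no passer, and nothing in the plan predicts it. Losses mainly among passers leave 86% to 87%.

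The 77% and 78% figures cannot both be right at one SD, and the sentence giving 78% does not state which SD it uses. At SD 0.90 the planned ANCOVA does not give 78% either.

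These results take the plan's difference, SD, correlation and 81% pass rate as given. The method agrees with the plan's main figures to within about two points, so differences of a point or two should not be over-read; a normal approximation puts 51/10 at 79.5%, against 78.1% here. The plan should be changed, but the ANCOVA itself is not in question.

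**What to change.** In 13.7, state the SD and the division of missing values behind every power figure, and say whether the 81% applies to all 72 or to those with data. Correct the 77% and 78%, or give the inputs that produce them. Replace the single 15% and 20% figures with a short table of power by number of non-passers with paired CD28 samples, such as the first table above, with the 36% row labelled a worst case. Replace the opening claim of excellent power with that range.

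In 6.5 and 11.4, make the already scheduled week-52 T-cell blood draw expected from every participant who stops OIT without withdrawing consent, in place of the present optional wording.

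The cost is a recalculated table, a few sentences, a few extra week-52 samples and less favourable stated power. I would not add a fixed minimum number of non-passers, extended enrolment or mandatory delta-adjusted imputation: these are trade-offs for the sponsor, and this finding does not require them.

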14.1. Source Data

Source documents and source data are considered to be the original documentation where subject information, visits consultations, examinations and other information are recorded. Documentation of source data is necessary for the reconstruction, evaluation and validation of clinical findings, observations and other activities during a clinical trial. In

this protocol, source data will be recorded onto paper CRFs at the time of collection. Skin test results will be recorded via adhesive tape transfer of the outline of any wheal(s) and/or erythema. Spirometry results will be recorded as printouts from the software package used to perform the testing.

14.2. Access to Source Data

The site investigators and site staff will make all source data available to the DAIT/NIAID, as well as to relevant health authorities. Authorized representatives as noted above are bound to maintain the strict confidentiality of medical and research information that may be linked to identified individuals.

15. Protocol Deviations

15.1. Protocol Deviation Definitions

Protocol Deviation – The investigators and site staff will conduct the study in accordance to the protocol; no deviations from the protocol are permitted. Any change, divergence, or departure from the study design or procedures constitutes a protocol deviation. As a result of any deviation, corrective actions will be developed by the site and implemented promptly.

Major Protocol Deviation (Protocol Violation) - A Protocol Violation is a deviation from the IRB approved protocol that may affect the subject's rights, safety, or well-being and/or the completeness, accuracy and reliability of the study data. In addition, protocol violations include willful or knowing breaches of human subject protection regulations, or policies, any action that is inconsistent with the NIH Human Research Protection Program's research, medical, and ethical principles, and a serious or continuing noncompliance with federal, state, local or institutional human subject protection regulations, policies, or procedures.

Non-Major Protocol Deviation - A non-major protocol deviation is any change, divergence, or departure from the study design or procedures of a research protocol that does not have a major impact on the subject's rights, safety or well-being, or the completeness, accuracy and reliability of the study data.

15.2. Reporting and Managing Protocol Deviations

The study site principal investigator has the responsibility to identify, document and report protocol deviations as directed by the study Sponsor. However, protocol deviations may also be identified during site monitoring visits or during other forms of study conduct review.

Upon determination that a protocol deviation has occurred, the study staff will a) notify the site Principal Investigator, b) notify the NIAID Project Manager, and c) will complete a Protocol Deviation form. The DAIT/NIAID Medical Monitor will make the decision as to whether the Deviation is major or not and what the impact of the Deviation on the study participant or the entire study may be. The study staff will submit the Protocol Deviation reports to the appropriate review bodies (IRB, DSMB, FDA etc.) and the principle investigator will review and approve the action plan that will be implemented as a result of the Protocol Deviation.

16. Ethical Considerations and Compliance with Good Clinical Practice

16.1. Statement of Compliance

This clinical study will be conducted using good clinical practice (GCP), as delineated in *Guidance for Industry: E6 Good Clinical Practice Consolidated Guidance*, and according to the criteria specified in this study protocol. Before study

initiation, the protocol and the informed consent documents will be reviewed and approved by the *IRB*. Any amendments to the protocol or to the consent materials will also be approved by the *IRB*, before they are implemented.

16.2. Informed Consent Process

The consent process will provide information about the study to a prospective participant and will allow adequate time for review and discussion prior to his/her decision. The principal investigator or designee listed on the FDA 1572 will review the consent and answer questions. The prospective participant will be told that being in the trial is voluntary and that he or she may withdraw from the study at any time, for any reason. All participants (or their legally acceptable representative) will read, sign, and date a consent form before undergoing any study procedures. Consent materials will be presented in participants' primary language. A copy of the signed consent form will be given to the participant. The consent process will be ongoing. The consent form will be revised when important new safety information is available, the protocol is amended, and/or new information becomes available that may affect participation in the study.

Appendix 1. Schedule of Events

Timepoint/Visit	Screen	Week 0 / Day 1	Every 2 wks (Weeks 0-28 or until maintenance reached)	Week 52	Week 58 /End of Study	Week 64 (Option al)	
Medical History	X						
Physical Assessment	X	X	X	X	X	X	
Con Meds	X	X	X	X	X	X	
Adverse Events	X	X	X	X	X	X	
Specific IgE/IgG4*	X			X	X	X	
Skin testing	X			X	X	X	
Blood for T cell studies*	X	X		X	X	X	
Urine pregnancy test	X						
Lung Function	X	X	X	X	X	X	
Diaries		X	X	X	X	X	
Inject Epi training	X			X	X		
Fecal samples	X			X	X		
DBPCFC	X			X TEST DESENSIT IZATION	X TEST SU	X TEST SU	
OIT (cashew or shrimp)		X	X				
QOL questionnaires*	X	X		X	X		

Appendix 2: Participant Disposition

If pregnancy or if hypotensive event related to study drug occurs, participants will be terminated from the study

Appendix 3: Dose Limiting Symptoms (CoFAR guidelines)

Challenges will be considered positive with the occurrence of any dose-limiting symptoms, which in the view of the PI indicate a true allergic reaction which should preclude the administration of any further doses.

During a dose escalation in clinic, the clinician will use the following criteria to determine if the dose was well tolerated and if the participant may go home on that dose.

As defined below, mild symptoms are not usually considered dose-limiting, although a combination of mild symptoms might lead to the cessation of a challenge or reduction in the dose that the participant is allowed to go home on at the discretion of the PI

All moderate and severe symptoms as defined below are considered dose-limiting.

Mild:

- Skin – limited (few) or localized hives, swelling (e.g., mild lip edema), skin flushing (e.g., few areas of faint erythema) or mild pruritus (e.g., occasional scratching)
- Respiratory – rhinorrhea (e.g., occasional sniffing or sneezing), nasal congestion, occasional cough, throat discomfort
- GI – mild abdominal discomfort (including mild nausea with or without decreased activity), isolated emesis thought to be secondary to gag

Moderate:

- Skin – systemic hives (e.g., numerous or widespread hives), swelling (e.g., significant lip or face edema), pruritus causing protracted scratching, more than a few areas of erythema or pronounced erythema
- Respiratory – throat tightness without hoarseness, persistent cough, wheezing without dyspnea

- GI – persistent moderate abdominal pain/cramping/nausea with decreased activity, vomiting

Severe:

- Skin – severe generalized urticaria/angioedema/erythema
- Respiratory – laryngeal edema, throat tightness with hoarseness, wheezing with dyspnea, stridor
- GI – severe abdominal pain/cramping/repetitive vomiting
- Neurological – change in mental status
- Circulatory – clinically significant hypotension

